7.6.5 Frequency of tumor re-evaluation

Frequency of tumor re-evaluation will be every 8 weeks in both arms and during planned study treatment breaks. In the case of suspected clinical progression or iUPD according to iRECIST, the next evaluation may be preponed to after 4 weeks.

Evaluation will be with routine CT of the thoracic/abdominal/pelvic cavities, preferably with contrast in the case of adequate renal function.

If brain or bone metastasis is suspected, supplemental MR evaluations may be undertaken. However, bone scans only need to be repeated when CR is identified in target disease or when progression in bone is suspected.

All target and non-target sites are assessed at each evaluation.

After discontinuation of protocol treatment, patients who have not progressed will still be re-evaluated every 8 weeks until end-of-study, as per protocol.

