6 STUDY FLOW CHART

Trial period	Screening phase		Treatment sequence ¹							
Scheduling window; visit (V), cycle (C), day(D)	V-1 (D -15 to D-1)	V0 (D -14 to D0)	V1 C1 D1 (±3 days)	V2 C2 D1 (±3 days)	V3 C3 D1 (±3 days)	V4 C4 D1 (±3 days)	V5 C5 D1 (±3 days)	V6 C6 D1 (±3 days)	V7 C7 D1 (±3 days)	V8 C8 D1 (±3 days)
Administrative procedures										
Informed consent	X									
Inclusion/exclusion criteria		X								
Tumor (K)RAS/BRAF mutation status ³		X								
Medical history		X								
Prior ⁴ and concomitant medication review		X	X	X	X	X	X	X	X	X
Post-study anticancer therapy status										
Questionnaires (QoL)		X								
Clinical procedures										
Review adverse events		X	X	X	X	X	X	X	X	X
Full physical examination ⁷		X ⁸								
Directed physical examination			X	X	X	X	X	X	X	X
Vital signs and weight		X	X	X	X	X	X	X	X	X
ECOG performance status		X	X	X	X	X	X	X	X	X
Survival follow-up										
Laboratory procedures										
Pregnancy test ⁹		X ¹⁰			X ¹⁰		X		X ¹⁰	
HIV, HBV, and HCV tests		X								
Laboratory analyses ¹³		X	X	X	X	X	X	X	X	X
Urine analysis ¹⁵		X	X	X	X	X	X	X	X	X
Treatment administration										
FLOX			X	X	X ¹⁶	X ¹⁶	X	X	X ¹⁶	X ¹⁶
Nivolumab					X ¹⁶	X ¹⁶			X ¹⁶	X ¹⁶
Evaluation procedure(s)										
CT ¹⁷		X ¹⁸					X			
Correlative study procedures										
Whole blood sampling			X							
Plasma and serum sampling			X		X		X		X	
PBMC sampling ¹⁹			X		X		X		X	
Functional MR liver acquisition ^{19,20}		X			X		X			
Liver/peritoneal biopsy sampling ²¹		X			X		X			

Trial period	Break period ²	End of study visit	Withdrawal visit (if applicable)	Post-treatment phase		
Scheduling window; visit (V), cycle (C), day(D)	Every 8 weeks	At the time of treatment discontin.	At the time of withdrawal	Safety follow-up (approx. D30 after discontin.)	Follow-up year 1 after discontin. (every 3 months ±7 days)	Survival follow-up
Administrative procedures						
Informed consent						
Inclusion/exclusion criteria						
Tumor (K)RAS/BRAF mutation status ³						
Medical history						
Prior ⁴ and concomitant medication review	X	X	X	X		
Post-study anticancer therapy status				X	X	
Questionnaires (QoL)	X ⁵	X				
Clinical procedures						
Review adverse events	X	X	X ⁶	X ⁶	X ⁶	
Full physical examination ⁷				X		
Directed physical examination	X	X	X			
Vital signs and weight	X	X	X	X		
ECOG performance status	X	X	X	X		
Survival follow-up						X
Laboratory procedures						
Pregnancy test ⁹	X ¹¹	X	X	X	X ¹²	
HIV, HBV, and HCV tests						

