7.7.3.2 Follow-up visits

When a subject discontinues study treatment, for whatever reason (PD/iCPD, unacceptable toxicity, or withdrawal of consent), the subject will move into the follow-up phase. The patient will be assessed every 3 months (± 7 days) the first year after discontinuation to monitor disease status. Every effort will be made to collect information regarding disease status until the start of a new anti-neoplastic therapy, disease progression, death, or end of the study. Information regarding post-study anti-neoplastic treatment will be collected if new treatment is initiated.

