7.7.3.3 Survival follow-up

Once a subject discontinues study treatment or starts a new anti-cancer therapy, the subject moves into the survival follow-up phase. We will monitor survival status every 6–12 months (by phone call, subject visit, contact with patient's general practitioner) until the end of the study. The survival status and, if applicable, the cause of death will be recorded.

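### After study treatment stops without progression, the protocol gives conflicting tumour-assessment rules, so PFS events can be lost or dated differently by site

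*Protocol*

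**What the plan says.** Several parts of the protocol govern the same patient, who is off study treatment and has not progressed.

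- **7.6.5 (tumour re-evaluation), once study treatment has stopped:** "patients who have not progressed will still be re-evaluated every 8 weeks until end-of-study". The same section names CT as the method.
- **7.7.3.2 (follow-up visits), for discontinuation for any reason:** "The patient will be assessed every 3 months (± 7 days) the first year after discontinuation to monitor disease status". No imaging method is named. Disease-status information is sought "until the start of a new anti-neoplastic therapy, disease progression, death, or end of the study".
- **7.7.3.3 (survival follow-up):** "Once a subject discontinues study treatment or starts a new anti-cancer therapy, the subject moves into the survival follow-up phase". Its content is: "We will monitor survival status every 6–12 months (by phone call, subject visit, contact with patient's general practitioner) until the end of the study".
- **7.7.4 (withdrawal or discontinuation):** patients who stop for reasons other than progression are followed for disease status until progression, non-study cancer treatment, withdrawal of consent or loss to follow-up. No interval is given. Survival-only information follows documented progression.
- **Chapter 6 (flow chart):** CT is marked in the break period and at the end-of-study visit. It is not marked at the withdrawal visit, the 30-day safety visit, the year-1 follow-up or the survival follow-up.

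The term end-of-study, which limits the 7.6.5 rule, has two meanings. The flow chart places the end-of-study visit at treatment discontinuation, whereas 7.8 defines end of study as last patient last visit.

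Protocol 7.6.1 and 10.4.1 and SAP 5.2 count first recorded progression or death as the PFS event. They censor other patients at the date last known alive and progression-free. The SAP repeats 8-weekly assessment but has no rule for off-treatment patients, new therapy or missed scans.

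**The concern.** PFS is the primary endpoint, and progression can be dated only if a scan is taken. A site using the flow chart as its working checklist would order no CT after discontinuation. A site reading 7.7.3.3 literally could telephone every 6–12 months. A site following 7.6.5 would scan every 8 weeks. The same patient could therefore have a PFS event at one site and be censored at another. A telephone contact also does not establish that a patient is progression-free, so the censoring date is unclear.

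The affected patients include those who stop for unacceptable toxicity, which Protocol 5.5 names as a reason to stop. The arms differ in exposure by design: 8 FLOX cycles per sequence against 4 FLOX and 4 nivolumab. Equal rates of stopping cannot be assumed. Protocol 5.5 and 7.8 also anticipate durable benefit after nivolumab is stopped, so off-treatment imaging bears on the trial's hypothesis.

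**Working it through.** **1. The plan's own figure (Protocol 10.1, SAP 2.3).** Inputs: HR 0.5, 80% power, 5% significance (two-sided assumed), 10% censoring. Freedman's formula gives d = (1.96 + 0.842)² × [(1 + 0.5)/(1 − 0.5)]² = 7.85 × 9 = 70.6, so 71 events. Then 71/0.9 = 78.9 patients, or 40 per arm, which reproduces the plan. The inflation 80/0.95 × 1.2 = 101 agrees with the stated 100 within rounding.

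**2. Delay if scans are 3-monthly.** The mean lag from progression to the next scan is half the interval: 8/2 = 4 weeks against 13/2 = 6.5 weeks. That is about 2.5 weeks more, in the affected patients only.

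**3. Loss by formula.** Removing 5% non-MSS cases leaves 95 patients. If a share f stop without progression and all their later events are lost, d = 95 × 0.9 × (1 − f), and Freedman power is Φ(√d × 0.5/1.5 − 1.96). The share f is an assumption.

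| f | Events | Power |
|---|---|---|
| 0% | 85.5 | 87% |
| 10% | 77.0 | 83% |
| 20% | 68.4 | 79% |
| 30% | 59.8 | 73% |

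This ignores patients still event-free at the data cut-off, so the event counts are optimistic.

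**4. Loss by simulation, with administrative censoring.** From the documents: medians of 9 and 18 months, the 8-week grid, and 18–30 months of follow-up (12 months of recruitment from 1 March 2018, last patient completed 1 September 2020). With 48 patients per arm and exponential PFS, the assumptions are that 10–30% per arm stop for toxicity at 2–9 months and that their hazard is 1.5 times higher afterwards. There were 3,000 trials per row; the Monte Carlo standard error is about √(0.8 × 0.2/3000) = 0.7 points.

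| Stops, control/experimental | Events, 8-weekly CT | Events, no CT after stopping | Power, 8-weekly CT | Power, no CT after stopping |
|---|---|---|---|---|
| 20/10% | 69.1 | 60.6 | 84% | 78% |
| 30/15% | 69.7 | 56.8 | 86% | 75% |
| 15/30% | 70.0 | 57.5 | 77% | 74% |
| 20/20% | 69.5 | 58.4 | 82% | 75% |

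The losses are 8.5 to 12.9 events and 3 to 11 points. An independent repeat gave about 7–12 events and 3–9 points. The 11 points in the 30/15 row are partly produced by the assumption: a raised hazard falling mainly on control patients enlarges the true effect and lifts the comparator to 86%. With the hazard unchanged, that row goes from 81% to 75%.

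A milder model, with 95 patients, 10% stopping in each arm and hazard unchanged, loses 66.8 − 63.4 = 3.4 events. Power falls from 80% to 77%.

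**5. The 3-monthly, first-year rule in 7.7.3.2.** Under the same kind of model, events fall by about 1–2 (for example 69.6 to 67.8) and power by up to about 2 points, which is close to simulation error.

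**6. Bias.** With equal medians and stopping unrelated to prognosis, the one-sided rejection rate stayed near 2.5%. In one informative example (equal medians, 10/30% stopping, hazard doubled after stopping), the hazard ratio was 1.08 with full CT and 1.01 without it.

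**The case against.** The strongest reply is that the protocol already contains the right rule. Section 7.6.5 is the section on tumour re-evaluation, and it covers off-treatment patients explicitly. Section 7.7.3.2 sets a visit interval and names no imaging, so 3-monthly visits need not cancel 8-weekly CT. Section 7.7.4 puts disease status first and survival-only follow-up after progression. Chapter 7 calls the flow chart a summary of procedures detailed in the text. On this reading, survival-only follow-up rests on one loose sentence in 7.7.3.3. This limits how often the loss is likely to occur. It does not remove the conflict: no passage gives 7.6.5 precedence, its end date is ambiguous, and a site working from the flow chart finds no CT to order.

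The no-CT figures are also an extreme. Deaths are PFS events and are recorded in survival follow-up, and 7.7.3.2 and 7.7.4 ask for disease status, so some events would still be captured.

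Three stronger readings are tempting and are not supported:

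- A reader might infer that PFS in these patients *is* delayed or lost. It is not, where sites follow 7.6.5.
- A reader might infer that the hazard ratio is biased. Unequal stopping related to prognosis could bias it, but the documents give no rates and the runs showed no material bias.
- A reader might infer that CT must continue after new anti-cancer therapy starts. Sections 7.3.5, 7.7.3.2 and 7.7.4 consistently end disease follow-up at that point, and 5.5 frames PFS as failure of treatment strategy. That is an estimand choice, not part of this contradiction.

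**Conclusion.** The conflict is real, unresolved and concerns ascertainment of the primary endpoint. Its effect depends on which text a site follows and on how many patients stop without progression, which the documents do not state.

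Assuming 10–30% per arm, complete absence of CT after discontinuation would cost about 7–13 of roughly 68–70 events and about 3–11 power points. The loss is smaller if few patients stop: about 3 events at 10% in each arm with unchanged hazard. The 3-monthly first-year rule alone costs about 1–2 events and up to about 2 points. All these figures count first recorded progression as the event, as 7.6.1 and 10.4.1 state. The wording in 5.5, progression on ongoing therapy, leaves it unclear whether progression after stopping would count.

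This should be fixed. The case rests on avoidable loss of events and on dating that depends on the site. It does not rest on demonstrated bias.

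**What to change.** Make 7.6.5 the single endpoint-assessment rule in both arms: patients without a PFS event continue CT every 8 weeks (±7 days) after stopping study treatment.

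- Add CT to the flow chart's post-treatment columns, for patients without a PFS event.
- Reconcile 7.7.3.2, 7.7.3.3 and 7.7.4 with it, so that discontinuation alone does not move a patient to survival-only follow-up.
- Give end-of-study one meaning in 7.6.5, 7.8 and the flow chart.
- Leave the handling of new anti-cancer therapy (7.3.5, 7.7.3.2, 7.7.4) to the sponsor's choice of estimand, and have the SAP state that choice and the matching censoring date.

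The cost is protocol and flow-chart wording, plus some scans that certain sites would otherwise have omitted. Section 7.6.5 already promises those scans. Scans not taken cannot be recovered at analysis, so the change is worth making early.

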7.6.6. Date of progression

This is defined as the first day when RECIST (v1.1) PD is observed in the control arm and after iRECIST iCPD is observed in the experimental arm.

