7.6 Tumor imaging and assessment of disease procedures

7.6.1 Evaluation of efficacy

The imaging assessments will be performed by CT, typically a thoracic/abdominal/pelvic CT scan. Tumor treatment response will be assessed according to RECIST v1.1 as the primary method and iRECIST as the secondary method. After baseline tumor assessments, evaluation of tumor response will be performed every 8 weeks (± 7 days). Additional MR scans or other radiologic evaluations will be performed if indicated.

All radiologic examinations will be transmitted to Study Radiologist at Akershus University Hospital within 1 working day after the scan is performed. A radiologist at the actual study center will evaluate the images for incidental findings that may have a therapeutic consequence (e.g., pulmonary embolism, immune therapy-related findings that require emergency actions).

Study Radiologist will be blinded to patient treatment, but will be informed about treatment breaks in the go-and-stop schedule. Study Radiologist will primarily assess tumor measures according to RECIST v1.1. If disease progression is concluded by means of RECIST v1.1, Study Radiologist will also assess tumor measures according to iRECIST. The radiology report will detail the criteria used for Clinical Investigator to make a decision about further study treatment (*c.f.*, [Paragraph 5.7.2.4](#)).

PFS will be calculated from the day of randomization to first recorded disease progression according to RECIST v1.1 or iRECIST when applicable, or death. Patients who have not had disease progression at the time of final analysis will be censored at the date last known to be alive and progression-free.

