CR	PD	SD provided minimum criteria for SD duration met, otherwise, PD	
CR	NE	SD provided minimum criteria for SD duration met, otherwise NE	
PR	CR	PR	
PR	PR	PR	
PR	SD	SD	
PR	PD	SD provided minimum criteria for SD duration met, otherwise, PD	
PR	NE	SD provided minimum criteria for SD duration met, otherwise NE	
NE	NE	NE	

* may consider PR providing initial "CR" likely PR on subsequent review – then original CR should be corrected. Recurrence of lesion after true CR is PD.

7.6.4 iRECIST

In the experimental arm, iRECIST will be used in the case of new lesion(s) or increase in size of known lesion(s), and if the patient is clinically deteriorating. This is categorized as *immune-unconfirmed progressive disease* (iUPD). An *immune-confirmed progressive disease* (iCPD) is only assigned if at next assessment after iUPD (4–8 weeks later) additional new lesions appear or an increase in size of new lesions is seen (≥ 5 mm for sum of new target lesion or any increase in new non-target lesion). The appearance of new lesions when none have previously been recorded can also confirm iCPD.

However, if progression is not confirmed but instead tumor shrinkage occurs (compared with baseline), which meets the criteria of *immune-complete response* (iCR), *immune-partial response* (iPR), or *immune-stable disease* (iSD), then the bar is reset so that iUPD needs to occur again (compared with nadir values) and then be confirmed (by further growth) at the next assessment, for iCPD to be assigned. If no change in tumor size or extent from iUPD occurs, then the time point response would again be iUPD. This approach allows atypical responses, such as delayed responses that occur after pseudoprogression, to be identified, further understood, and better characterized.

Response criteria are essentially based on a set of measurable lesions identified at baseline as target lesions, and, together with other lesions that are denoted as non-target lesions, followed until disease progression.

For direct comparison of iRECIST with RECIST v1.1 [Seymour *et al.*, 2017], please refer to **Appendix 2**.

iCR or iPR may be claimed only if the criteria for each are met at a subsequent time point at least 8 weeks later.

Assignments of timepoint response using iRECIST:

	Timepoint response with no previous iUPD in any category	Timepoint response with previous iUPD in any category
Target lesions: iCR; non-target lesions: iCR; new lesions: no	iCR	iCR

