#### 5.2. Analysis methods

*Main statistical analyses.* The main statistical analysis is planned after the last patient has fulfilled the pre-defined follow-up period. PFS will be calculated from the day of randomization to first recorded disease progression according to RECIST v1.1 or when applicable iRECIST, or death. Patients who have not had disease progression at the time of final analysis will be censored at the date last known to be alive and progression-free. The analyses will compare the treatment groups in total as well as groups stratified by primary tumor sidedness and (K)RAS/BRAF mutation status.

*Interim analyses.* Interim analyses will apply to data on safety, tolerability, possible detrimental effects, and curative outcomes, and will be based on purely clinical judgment by the External Data and Safety Monitoring Committee. These types of data will be reported as the number of events.

*Descriptive statistics.* Demographic and clinical characteristics will be presented as means and standard deviations, medians with minimum and maximum values, or frequencies and percentages, as appropriate. Further statistical analyses will be separated to primary analyses, including only comparison of primary end point between two treatment arms, and secondary analyses, including stratified analyses on primary and secondary end points as well as number of analyses on secondary end points.

*Primary analysis.* Median PFS time will be compared between study arms by drawing Kaplan-Meier survival curves and performing log-rank test. HR with the corresponding 95% CI and p-values will be estimated by Cox proportional hazards model.

*Secondary analyses.* Distribution of PFS times stratified by the primary tumor sidedness and (K)RAS/BRAF mutation status will be illustrated graphically by Kaplan-Meier curves and compared by log-rank test. To assess the hazard rates for disease progression within each strata, Cox proportional hazards model will be estimated and, if appropriate, adjusted for relevant covariates. The results will be presented as HR with the corresponding 95% CI and p-values.

Safety. The number of serious adverse events (SAE) will be summarized and presented by trial arm. In addition, information will be given on the number of SAE per participant, together with details on the causality, expectedness, and outcome of each SAE experienced. Summaries of suspected unexpected serious adverse reaction (SUSAR) events will also be presented by trial arm.

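### Protocol 7.6.6 dates progression by different rules in the two arms; if it governs, only experimental-arm progressions are delayed, and the chance of a false favourable PFS result rises from about 2.5% to as much as 6–12%

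*Protocol*

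**What the plan says.** The only explicit date rule is Protocol 7.6.6, which takes progression as "the first day when RECIST (v1.1) PD is observed in the control arm and after iRECIST iCPD is observed in the experimental arm".

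Protocol 7.6.4 brings in iRECIST for the experimental arm. There, confirmed progression (iCPD) "is only assigned if at next assessment after iUPD (4–8 weeks later) additional new lesions appear" or new lesions grow. Disease that neither grows nor shrinks is not confirmed: "If no change in tumor size or extent from iUPD occurs, then the time point response would again be iUPD". Protocol 7.6.5 sets scans every 8 weeks in both arms and makes an earlier scan at 4 weeks optional. No passage moves a confirmed iCPD back to the date of the first unconfirmed progression (iUPD). Protocol 7.6.3, by contrast, does move equivocal RECIST progression back to the earlier scan once it is documented.

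Other passages are less specific. Protocol 7.6.1 states: "Tumor treatment response will be assessed according to RECIST v1.1 as the primary method and iRECIST as the secondary method". SAP 5.2 runs PFS from randomization to the first recorded progression "according to RECIST v1.1 or when applicable iRECIST, or death"; Protocol 7.6.1 and 10.4.1 say the same in substance. None of these names an arm or says when iRECIST applies. SAP 5.4 plans no further analyses, so no analysis using one criterion in both arms is foreseen.

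**The concern.** Under 7.6.6 the same CT finding is an event on the day of the scan in the control arm. In the experimental arm it is an event only once a later scan confirms it. The delay comes from the measurement rule, not from the treatment, and it always runs in the experimental arm's favour. The primary analysis is a log-rank comparison of these dates with about 50 patients per arm, so a delay of 4–8 weeks against a control median of 39 weeks is not negligible. The end date of duration of response (DOR) has the same asymmetry, because DOR also ends at progression. At stake is the false-positive rate of the primary comparison and the size of the reported hazard ratio.

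**Working it through.** **The plan's own figure.** Protocol 10.1 and SAP 2.3 give HR 0.5, 80% power, 5% significance, the log-rank test, 10% censoring and 40 per arm. Freedman's formula, two-sided, gives (1.96 + 0.84)² × [(1 + 0.5)/(1 − 0.5)]² = 7.85 × 9 = 70.6, so 71 events. Then 71/0.90 = 78.9, or 79 patients and 40 per arm, which matches. The increase to 100 is also consistent: 80/0.95 × 1.2 = 101, or 80 × 1.05 × 1.2 = 100.8. One-sided versions give only 29–32 per arm. The level is therefore two-sided 5%, and the benchmark for a false result favouring the experimental arm is 2.5%.

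**Inputs from the documents.** Control median 9 months; 50 per arm, or about 48 after removing 5% non-MSS cases (50 × 0.95 = 47.5); accrual 12 months; first enrolment 1 March 2018 and last patient completed 1 September 2020, which is 30 months; scans every 8 weeks; confirmation after 4–8 weeks.

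**Assumptions not in the documents.** Uniform accrual; one exponential time to strategy failure, ignoring the go-and-stop schedule; the share of progressions that wait for confirmation; the share of PFS events that are deaths.

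**Shift of the median.** 9 months × 52.18/12 = 39.1 weeks. Adding 4 or 8 weeks gives 43.1 or 47.1 weeks. The ratios are 39.1/43.1 = 0.91 and 39.1/47.1 = 0.83.

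**Simulation with no drug effect.** Both arms have an exponential median of 9 months. Progression is rounded up to the next 8-week scan, experimental-arm progression dates are then moved later, and follow-up stops at 30 months. The test is an unstratified log-rank test, counting results beyond 1.96 in favour of the experimental arm. The table uses 50 per arm and 8,000 trials per row (4,000 for the 16-week row). The Monte Carlo standard error is at most about 0.4 points in the 8,000-trial rows. The HR is the mean one-step log-rank estimate.

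| Delay in the experimental arm | False favourable result | Apparent HR |
|---|---|---|
| None (same rule in both arms) | 2.4% | 1.01 |
| 4 weeks, all progressions | 6.1% | 0.91 |
| 4 or 8 weeks, half each | 7.9% | 0.88 |
| 8 weeks, all progressions | 12.4% | 0.82 |
| 8 weeks in 25% / 50% / 75% | 4.0% / 5.9% / 8.3% | 0.95 / 0.91 / 0.87 |
| 4 weeks in 50% | 3.2% | 0.97 |
| 8 weeks, 10% / 20% of events are deaths (not moved) | 10.4% / 9.2% | 0.84 / 0.86 |
| 4 weeks, 10% / 20% of events are deaths (not moved) | 5.7% / 5.1% | 0.92 / 0.93 |
| 16 weeks (iUPD persists), all progressions | 34% | 0.69 |

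A separate run with 48 per arm and 4,000 trials gave 2.6%, 5.9% (HR 0.91) and 11.6% (HR 0.83) for no delay, 4 weeks and 8 weeks. Moving the cutoff to 24 or 42 months changes the 8-week figure only to 12.7% or 11.4% (4,000 trials each).

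**Progressions that are never confirmed.** With 48 per arm and an 8-week delay, if an assumed 10% or 20% of experimental-arm progressions are censored at the first PD scan, the figures are 22% (HR 0.75) and 35% (HR 0.66). If those patients are instead confirmed one scan later, they are 13% and 15%. If they become events only at death, with an assumed median of 26–52 weeks after PD, they are 17–22% and 22–35%.

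**With a real but smaller effect.** For a true experimental median of 12 months, an 8-week delay raises the chance of significance from 25% to 50% (4,000 trials).

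**The case against.** The strongest reply is that the general definition is neutral between arms. It can be read as RECIST v1.1 in both arms, and the SAP contains no date rule by arm. That stands to this extent: the bias arises only if 7.6.6 governs. But 7.6.6 is the only passage that fixes a date, and 7.6.4 points the phrase about applicability at the experimental arm. If the neutral reading is intended, 7.6.6 still has to change. For the same reason a reader might infer that 7.6.6 flatly contradicts 7.6.1. It does not: 7.6.1 itself admits iRECIST for PFS, and its ranking of methods concerns tumor response. The passages are unreconciled.

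A second reply is that not every event is delayed. That is correct: deaths are PFS events and do not move, and the share of progressions awaiting confirmation is unknown. The range in the table reflects this.

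A third is that 7.6.6 might mean the iUPD date once confirmed. The delay then disappears, but unconfirmed progressions remain events in the control arm only. With an assumed 10% or 20% unconfirmed and censored, the false favourable rate is 6.7% or 17%.

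A fourth is that PFS here means failure of the treatment strategy, and Protocol 5.7.2.4 ends treatment at confirmed progression. This is an argument for choosing an iRECIST date in both arms, not for measuring the arms differently.

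A reader might also infer that a radiologist blinded to arm could not apply the rule. The documents do not support that. Under 7.6.1 the blinded radiologist reads RECIST v1.1 first and adds iRECIST whenever RECIST shows progression, with no arm named. Both dates can be recorded blind and the rule applied at analysis.

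**Conclusion.** The concern holds, provided 7.6.6 governs. With no drug effect, the chance of a significant result favouring the experimental arm rises from about 2.5% to about 6% (4 weeks) or 12% (8 weeks) if all progressions are delayed, and to about 4–8% if 25–75% are delayed by 8 weeks. These figures rest on a single exponential time to strategy failure, which only approximates the go-and-stop design.

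The 22% and 35% figures should not lead. They depend on a share of unconfirmed progressions and a censoring rule that the documents do not give.

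Nor do the documents support the inference that any positive result would be an artefact. At 4–8 weeks, about 88–94% of trials with no effect still would not favour the experimental arm, and the delay alone produces an apparent HR of about 0.82–0.91, far from the design value of 0.5. The problem is an inflated error rate and an exaggerated effect on the primary endpoint, always in the same direction, with no planned analysis that would show it.

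**What to change.** State one progression-date rule for both arms in Protocol 7.6.6 and SAP 5.2, and use it for primary PFS and for the end date of DOR. One suitable choice is the first RECIST v1.1 PD under the on-therapy failure definition of Protocol 5.5. Align 7.6.1, 7.6.4 and 10.4.1 with it, and remove or define the phrase about when iRECIST applies.

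Add to SAP 5.4 a sensitivity analysis of iRECIST-based PFS in both arms, dated at the first iUPD that is later confirmed. Say how patients without a confirming scan are handled, identically in both arms. This matters because 7.6.5 guarantees continued scanning after treatment stops only for patients who have not progressed.

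The cost is wording. RECIST v1.1 is already read first for every patient, the sample size does not change, the primary rule needs no extra scans, and treatment decisions after suspected progression stay as they are. With the same rule in both arms the simulated false favourable rate is 2.4%. The downside is that true pseudoprogression in the experimental arm counts as an event in the primary analysis; the sensitivity analysis shows how often that happens.
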